8.1.5. Electrocardiogram

Electrocardiogram assessment will be performed overtime during the study. Descriptive statistics of the observed values for numeric parameters will be summarized by cohort and overall, for example, ventricular rate (beats/min), P-R interval(msec), QRS duration (msec), Q-T interval (msec) and Q-Tc interval (msec). The number and percentage of subjects will be summarized by treatment cohort and overall for categorical parameters, for example, normal sinus rhythm, QRS axis and ECG interpretation. Corresponding listing will be provided.

8.1.6. Echocardiogram

Echocardiogram assessment will be performed at Screening, Week 48, Month 24, and Month 36/end of study visit or early termination visit if applicable. Descriptive statistics of the observed values for left ventricular ejection fraction (%) will be summarized by cohort and overall. The number and percentage of subjects will be summarized by treatment cohort and overall for categorical results (normal, abnormal not clinically significant, abnormal clinically significant). Corresponding listing will be provided.

8.1.7. Concomitant Medications

The Principal Investigator will record all concomitant medications, including over-the-counter medicinal products, dietary supplements, herbal medications, and medications given in treatment of AEs, taken by a subject from Screening throughout the course of the study on the concomitant medications page in the subject's CRF. Subjects who received ERT prior to study enrollment should continue to receive ERT as per standard of care, except during the week of the SB-318 infusion, and such treatment should be recorded as concomitant medication. Treatment with prednisone or equivalent corticosteroid and pre-treatment with acetaminophen and diphenhydramine hydrochloride should also be recorded as concomitant medication. All CRF recorded concomitant medications will be used in summary and listing.

Concomitant medications will be coded using the WHO Drug Dictionary. The dictionary will be updated throughout the life of the project to allow for the most recent version of the dictionary to be used. The medication names will be coded according to the Anatomical Therapeutic Chemical (ATC) class level 4 and preferred terms provided in the dictionary.

Concomitant medications will be summarized by providing the number and percentage of subjects by ATC class level 4 and preferred term for each treatment cohort and overall. ATC classes will be sorted in decreasing order of frequency based on the total number of subjects who take each medication in the total column, while preferred terms within each drug class will be presented in decreasing order of frequency. In addition, the total number of medications and the number and percentage of subjects receiving at least 1 concomitant medication will also be presented. If a subject has multiple medications for a given preferred term the subject will only be counted once.

All concomitant medications will be presented in a listing.

8.1.8. Monitoring of chimerism in post-HSCT subjects

Chimerism assay will be performed at Baseline, Weeks 12 and 48, Month 36/end of study visit or early termination visit if applicable. Descriptive statistics of the observed values for T-cells % recipient, T-cells % donor, B-cells % recipient, B-cells % donor, myeloid cells % recipient and myeloid % donor will be summarized by cohort and overall. Corresponding listing will be provided.

8.1.9. Neurological cranial nerve exam and muscle strength testing

The neurological cranial nerve exam and muscle strength testing will be conducted over time during the study. The neurological cranial nerve exam includes oculomotor nerve, trochlear nerve and abduces nerve assessment, facial nerve assessment, accessory nerve assessment, and hypoglossal assessment. Each assessment has outcome categorized into normal, abnormal non clinical significant and abnormal clinical significant. The muscle strength testing includes scapular assessment, shoulder abduction, elbow flexion, and hand extension. The test result has 6 categories: no contraction, visible/palpable muscle contraction but no movement, movement with gravity eliminated, movement against gravity only, movement against gravity with some resistance, and movement against gravity with full resistance. The number and percentage of subjects in each test result category will be summarized by scheduled visit. Corresponding listing will be displayed.

8.1.10. MRI of Liver

Liver mass will be evaluated through MRI of liver at Screening, Week 48, Month 24 and Month 36/end of study visit or early termination visit if applicable. MRI findings are categorized in to normal and abnormal. The number and percentage of subjects in each category will be summarized by scheduled visit. Corresponding listing will be provided.

8.2. Secondary Endpoint Analysis

The secondary analysis is to evaluate change from baseline over time for the endpoints mentioned in Section 3.2.2.

At each sampling time point, the actual value and the change from baseline for IDUA activity and GAG levels in urine will be summarized using descriptive statistics by treatment cohort.

8.2.1. Plasma and leukocyte IDUA activity

Plasma and leukocyte IDUA activity will be assessed over time through the end of study visit or early termination visit if applicable. Descriptive statistics of the observed values and change from baseline will be provided at the scheduled visits. A corresponding listing and summary table will be provided.

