Stopping Rules	
The SMC will be convened to assess whether changes should be made to the study or whether the study should be stopped if any of the following criteria are met:
 

• Completion of a cohort.

• Any one Grade 3 or higher AE, or any two Grade 2 AEs in the same system organ class that persist for more than 2 weeks with therapy, provided these AEs are not related to the primary MPS I disease or treatment of the MPS I disease.

• SAE not related to the primary MPS I disease.

• Death of a subject.

• Development of a malignancy.

 
The study may also be stopped for any of the following reasons:
 

• Sangamo Therapeutics, Inc. (Sangamo), in consultation with the SMC or Regulatory Agency, decides for any reason that subject safety may be compromised by continuing the study.

• Sangamo decides to discontinue development of SB-318.

 
When no further enrolling or dosing decisions are required of the SMC, the SMC will no longer meet. Sangamo will continue to review subject safety data on an ongoing basis.

Sample Size	
This study will enroll up to a total of 27 subjects (1 subject in Cohort 1 and 2 subjects in each of the other 6 cohorts, with potential enrollment of approximately 2 additional subjects in any cohort). To obtain an evaluable sample size, subjects who prematurely discontinue the study prior to the 12 months of study follow-up (i.e., subjects who were enrolled but not dosed, or were lost to follow-up) may be replaced at the discretion of Sangamo.

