Almost all patients with MPS IH undergo HSCT. If patients are diagnosed early (at <2.5 years), therapeutic intervention by HSCT can prevent or reverse most clinical features including the neurocognitive symptoms. Unfortunately, the mortality rate after HSCT has been reported to be 15%, and survival rate with successful engraftment is 56%, although recent improvements in HSCT procedure have improved overall outcomes ([Boelens et al. 2013](#)).

ERT has been shown to improve pulmonary function, hepatosplenomegaly, and exercise capacity, and to lead to improved health-related quality of life. ERT should be instituted as early as possible. However, drawbacks of ERT include the need for life-long treatment; development of neutralizing antibodies; inability to cross the blood brain barrier; continued cardiac, orthopedic, and ocular complications; and the inconvenience of weekly intravenous (IV) infusions. These drawbacks underscore the urgent need to develop a broader array of curative therapies for MPS I.

The objective and rationale for the proposed SB-318 investigational therapy is to abrogate or decrease the need for ERT using *in vivo* genome editing. The proposed treatment employs recombinant adeno-associated virus (rAAV) comprising engineered zinc finger nucleases (ZFNs) to site-specifically integrate a corrective copy of the human iduronidase enzyme (IDUA)

[figure not shown]
transgene into the genome of subjects' own hepatocytes *in vivo*. Integration of the hIDUA transgene is targeted to intron 1 of the albumin locus, resulting in stable, high level, liver-specific expression and secretion of hIDUA into the blood. Placement of the hIDUA transgene under the control of the highly expressed endogenous albumin locus is expected to provide permanent, liver-specific expression of hIDUA for the lifetime of an MPS I patient.

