#### **9.18 Chimerism Assay**

The chimerism assay is a routine post-transplant monitoring tool to evaluate the ratio of donor-to-recipient white blood cells in peripheral blood. The assay will be performed on blood samples in post-HSCT subjects to evaluate the safety of SB-318 with respect to any potential impact on the donor graft. Baseline chimerism prior to SB-318 will be established by analyzing blood samples in conjunction with HSCT-donor specific and subject-specific genetic markers as provided by the original transplant center. In instances where this data is not available from the transplant center, baseline chimerism can be determined from buccal swabs and peripheral blood samples analyzed in parallel. For details, refer to the Laboratory Manual.

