- e. Liver panel will be performed twice a week for the first 20 weeks post-SB-318 infusion and may be remotely. Blood samples will be drawn 2-4 days apart when possible, except for the first week when it will be drawn on the Day 1 and Day 7 visits. Liver function tests will subsequently be conducted at all indicated study visits.
- f. For adult subjects (cohorts 1 through 3), the assay will be performed on blood or saliva samples. For post-transplant subjects, the assay will be performed on saliva samples only. For pediatric subjects (cohorts 4 through 7), saliva samples are preferred.
- g. For post-HSCT patients only.
- h. During Screening, samples for GAG testing in urine will be collected on 3 separate days, each collection occurring at least 7 days after the previous. All samples for GAG testing in the urine must be collected at least 7 days after ERT administration [+/- 1 day] but prior to the next ERT infusion.
- i. For IDUA/GAG testing in blood, samples must be obtained 7 days after ERT administration (+/- 1 day) and prior to the next ERT infusion. GAG and IDUA levels in blood will both be measured concurrently from the same blood sample.
- j. Each type of sample (plasma, saliva, urine, stool, semen) will be collected until 3 consecutive specimens of that sample type are reported as negative or undetectable for vector genome. Collection of semen samples may be waived for male pediatric subjects (cohorts 4 through 7) at the discretion of Principal Investigator.
- k. As permitted by subject's capacity. Neurocognitive abilities testing in pediatric subjects will be done by VABS-II and by WASI-II, WPPSI-IV, or BSID-III, as appropriate based on the Neurocognitive Abilities Assessment performed at Screening.
- l. Baseline MRI of brain and cervical spine may be obtained at Screening (together with MRI for liver) instead of at Baseline at the discretion of the Principal Investigator.
- m. Should prednisone or equivalent corticosteroid treatment be continued or repeated due to increased transaminase activity, the ACTH stimulation test will be repeated at the end of taper. Vital signs should be monitored and recorded every hour during the ACTH stimulation test.
- n. Unless contraindicated by a Principal Investigator or physician.
- o. May be waived for pediatric subjects (cohorts 4 through 7) at the discretion of the Principal Investigator to minimize required blood volumes.
- p. See [Appendix 3](#).

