In this study, the objective and rationale for the proposed SB-318 investigational therapy is to abrogate or decrease the need for ERT using *in vivo* genome editing. The proposed treatment employs recombinant adeno-associated virus (rAAV) comprising engineered zinc finger nucleases (ZFNs) to site-specifically integrate a corrective copy of the human iduronidase enzyme (hIDUA) transgene into the genome of subjects' own hepatocytes *in vivo*. Integration of the hIDUA transgene is targeted to intron 1 of the albumin locus, resulting in stable, high level, liver-specific expression and secretion of hIDUA into the blood. Placement of the hIDUA transgene under the control of the highly expressed endogenous albumin locus is expected to provide permanent, liver-specific expression of hIDUA for the lifetime of an MPS I patient.

The purpose of the Statistical Analysis Plan (SAP) is to describe the analyses and data presentations for Sangamo's protocol SB-318-1502 (Amendment version 7). This SAP outlines the types of analyses that will address the study objectives and explains in detail how the data will be handled and analyzed. It contains the definitions of analysis sets and statistical methods for the analysis of endpoints. Since this is an exploratory Phase I study, all analyses will be descriptive and exploratory in nature. No hypotheses testing will be carried out.

2. Objectives

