4.1. Sample Size

This study will enroll up to 27 subjects (1 subject in Cohort 2 and 2 subjects in each of the other 6 cohorts with potential enrollment of approximately 2 additional subjects in any cohort).

The sample size for this study was not based on statistical considerations, but is considered sufficient to provide preliminary assessments of the safety and tolerability of SB-318 in subjects with MPS I, as well as biochemical changes related to the pathophysiology of MPS I. Subjects who prematurely discontinue the study prior to the 12 months of study follow-up (i.e., subjects who were enrolled but not dosed, were lost to follow-up, or discontinued prematurely for another reason) may be replaced at the discretion of Sangamo.

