SB-318 5.00E+13 vg/kg	XXXXXX	XXX	XXX	XXX

Source Data: Listing 16.2.4.2

<DIRECTORY PATH>PROGRAM NAME Executed: DDMMYYYY hh:mm

Table 14.2.1
Change from Baseline in Plasma and Leukocyte IDUA Activity
Safety Set

Parameter: Alpha Iduronidase Plasma (nmol/hr/mL)

Visit	SB-318 1.00E+13 vg/kg (N=xx)		SB-318 5.00E+13 vg/kg (N=xx)		Total (N=xx)	
	Actual Value	Change From Baseline [1]	Actual Value	Change From Baseline [1]	Actual Value	Change From Baseline [1]
BASELINE						
n	xx		xx		xx	
MEAN (SD)	xx.x (xx.xx)		xx.x (xx.xx)		xx.x (xx.xx)	
MEDIAN	xx.x		xx.x		xx.x	
MIN, MAX	xx, xx		xx, xx		xx, xx	
VISIT X						
n	xx	xx	xx	xx	xx	xx
MEAN (SD)	xx.x (xx.xx)	xx.x (xx.xx)	xx.x (xx.xx)	xx.x (xx.xx)	xx.x (xx.xx)	xx.x (xx.xx)
MEDIAN	xx.x	xx.x	xx.x	xx.x	xx.x	xx.x
MIN, MAX	xx, xx	xx, xx	xx, xx	xx, xx	xx, xx	xx, xx

..
Note: Baseline is defined as last non-missing measurement prior to dosing.

[1]Change from baseline: post-baseline value - baseline value. For the change from baseline, only subjects with a value at both baseline visit and the specific post-baseline visit are included.

Source Data: Listing 16.2.9.3

<DIRECTORY PATH>PROGRAM NAME Executed: DDMMYYYY hh:mm

Prog Notes: Repeat for Alpha Iduronidase Leukocyte (nmol/hr/mL) parameter. Post baseline visits include Day 7, Weeks 2, 4, 6, 8, 12, 16, 20, 24, 36, 48, Months 15, 18, 21, 24, 27, 30, 33, 36/ EOS, or Early Termination Visit if applicable.

Table 14.2.2
Change from Baseline in Urine GAG Levels and Urine GAG/Creatinine Ratio
Safety Set

Parameter: Total Glycosaminoglycans (GAGs) (mg/mmol creatinine)

Visit	SB-318 1.00E+13 vg/kg (N=xx)		SB-318 5.00E+13 vg/kg (N=xx)		Total (N=xx)	
	Actual Value	Change From Baseline [1]	Actual Value	Change From Baseline [1]	Actual Value	Change From Baseline [1]
BASELINE						
n	xx		xx		xx	
MEAN (SD)	xx.x (xx.xx)		xx.x (xx.xx)		xx.x (xx.xx)	
MEDIAN	xx.x		xx.x		xx.x	
MIN, MAX	xx, xx		xx, xx		xx, xx	
VISIT X						
n	xx	xx	xx	xx	xx	xx
MEAN (SD)	xx.x (xx.xx)	xx.x (xx.xx)	xx.x (xx.xx)	xx.x (xx.xx)	xx.x (xx.xx)	xx.x (xx.xx)
MEDIAN	xx.x	xx.x	xx.x	xx.x	xx.x	xx.x
MIN, MAX	xx, xx	xx, xx	xx, xx	xx, xx	xx, xx	xx, xx

...
Note: Baseline is defined as last non-missing measurement prior to dosing.

[1]Change from baseline: post-baseline value - baseline value. For the change from baseline, only subjects with a value at both baseline visit and the specific post-baseline visit are included.

Source Data: Listing 16.2.9.4

<DIRECTORY PATH>PROGRAM NAME Executed: DDMMYYYY hh:mm

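### Leukocyte IDUA is summarised without regard to prior HSCT, so observed values can reflect graft enzyme, and changes can be distorted by chimerism drift or dilution

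*SAP*

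**What the plan says.** **Analysis.** Change from baseline in blood IDUA activity is a secondary endpoint (Protocol 13.5, SAP 3.2.2). Protocol 9.29 lets it be measured in plasma, leukocytes or other blood components, with no condition for transplanted subjects. SAP 8.2.1 fixes the two matrices: "Plasma and leukocyte IDUA activity will be assessed over time through the end of study visit or early termination visit if applicable". Table 14.2.1 shows plasma IDUA first, as observed value and change from baseline, with a column for each dose level and a Total. Its programming note adds: "Repeat for Alpha Iduronidase Leukocyte (nmol/hr/mL) parameter" SAP 4 makes cohort and overall the default grouping. Neither 8.2.1 nor the table separates, excludes or flags post-HSCT subjects.

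**Population.** No criterion in Protocol 4.1 or 4.2 bars prior HSCT, and the protocol plans for such subjects. Section 9.18 explains: "The chimerism assay is a routine post-transplant monitoring tool to evaluate the ratio of donor-to-recipient white blood cells in peripheral blood". For the genetic tests, Appendix 1 footnote f says: "For post-transplant subjects, the assay will be performed on saliva samples only".

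**Where HSCT information appears.** Chimerism is a stand-alone safety summary (SAP 8.1.8, Table 14.3.8). HSCT history is in Listing 16.2.3.2 and chimerism by subject in Listing 16.2.2.6. HSCT status is not in the demographics and baseline table (14.1.2), nor in the IDUA listing (16.2.9.3).

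**The concern.** SB-318 is designed to edit hepatocytes, which then secrete IDUA into the blood. Donor leukocytes carry an intact IDUA gene whether or not SB-318 works, so enzyme made in those cells is not a drug effect. The protocol acts on this for gene sequencing and the SNP assay, where it rules out blood after transplant. The SAP has no counterpart for leukocyte enzyme activity.

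Three things can follow in Table 14.2.1. The observed-value columns can show activity that comes from the graft. The change columns can move because the donor share of white cells moves. And a real gain can be diluted if donor cells already at normal activity do not register it. Cohorts are planned at one or two subjects, so a single transplanted subject can be all or half of a dose column. A reader of the table would not know that such a subject is in it.

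**Working it through.** **1. The plan's own figure.** The only design figure is the maximum enrolment. The protocol synopsis gives "1 subject in Cohort 1 and 2 subjects in each of the other 6 cohorts, with potential enrollment of approximately 2 additional subjects in any" of the seven: 1 + 6×2 = 13 planned, plus 7×2 = 14 possible additions, total 27. This reproduces the stated maximum. (Protocol 13.1 and SAP 4.1 attach the single subject to Cohort 2, where the cohort tables say Cohort 1; the count is the same.) SAP 4.1 says "The sample size for this study was not based on statistical considerations", so there is no power or error rate to recompute.

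**2. Model for the illustration.** Leukocyte activity L = f×D + (1 − f)×R, where f is the donor fraction, D donor-cell activity and R recipient-cell activity.

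- D = 6 to 71.4 nmol/hr/mg: the normal range in the mock row of Listing 16.2.9.3, assumed to apply to donor cells.
- R = 0: assumed, for deficient cells.
- SB-318 effect = 0: set, to isolate the graft.
- f: not given in the documents. I use 1 for a fully engrafted subject and a 10-point shift for drift. Both are assumptions.

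The note to Table 14.2.1 gives the leukocyte unit as nmol/hr/mL, but the listing has nmol/hr/mg. The figures below use the listing's unit.

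**3. Observed values.** With one fully engrafted and one non-HSCT subject, the mean is (D + 0)/2: 6/2 = 3.0 to 71.4/2 = 35.7 nmol/hr/mg. With one such subject among the five planned adults (1 + 2 + 2), the Total mean is 6/5 = 1.2 to 71.4/5 = 14.3.

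**4. Change from baseline.**

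- Stable graft: (f − f)×D = 0. It cancels.
- 10-point shift: 0.10×6 = 0.6 to 0.10×71.4 = 7.1 in that subject, in either direction. The two-subject mean moves by half of this, 0.3 to 3.6.
- Dilution: if donor cells cannot show a gain, one HSCT subject in two leaves (2 − 1)/2 = half of the mean gain seen in non-HSCT cells; two of two leave none.

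**5. Can drift be judged from the planned outputs?** The note to Table 14.2.1 lists 19 scheduled post-baseline visits: Day 7, ten week visits and eight month visits. SAP 8.1.8 schedules chimerism at three post-baseline visits (Weeks 12 and 48, Month 36/EOS), plus early termination if it applies. Most leukocyte IDUA values therefore have no chimerism value at the same visit.

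**6. After the change.** The graft contribution to a non-HSCT leukocyte row is 0 in both observed value and change.

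**The case against.** The strongest reply is that the endpoint is change from baseline, where a stable graft drops out, and that plasma IDUA is already tabulated for every subject, separately from leukocytes. The study is also descriptive: "No hypotheses testing will be carried out". Table 14.2.1 prints the minimum and maximum, and with two subjects these are the two values. Listings 16.2.9.3, 16.2.2.6 and 16.2.3.2 already hold the IDUA results, chimerism and HSCT history by subject. On this view, only side-by-side display is missing.

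Much of this stands. It confines the point to the leukocyte half, and within the change columns to drift or dilution. It does not remove the point. Observed values are a planned output (SAP 8.2), and no cancellation occurs there. The minimum and maximum show that two values differ, not that one comes from a graft. To discover that, a reader must cross-match three listings.

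The size is also open to attack, fairly. The 6 to 71.4 range comes from an example row in a shell. No document gives a 10-point drift. Chimerism is reported by T-cell, B-cell and myeloid lineage, so there is no single donor fraction to multiply.

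A reader might infer from Protocol 1.1, which says "Almost all patients with MPS IH undergo HSCT" and puts severe disease at 50-80% of MPS I, that transplanted subjects will be common here. The documents do not support that. Those statements describe the disease population. The same section reports 15% mortality after HSCT and 56% survival with engraftment, and Protocol 1.6 names ERT as the treatment of choice for the targeted patients. The number of HSCT subjects enrolled is not given and could be zero.

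**Conclusion.** The point holds for the leukocyte half of the blood IDUA endpoint. As planned, observed leukocyte values can reflect graft enzyme in any column that contains a post-HSCT subject. The change columns are affected only if chimerism drifts, or if donor cells already at normal activity dilute a gain.

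The sizes (an observed mean of 3.0 to 35.7 nmol/hr/mg for one fully engrafted subject of two, and a shift of 0.3 to 3.6 in the two-subject mean change for a 10-point drift) are illustrations. They rest on the assumed D, R, f and zero drug effect, and on there being such a subject at all.

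A reader might go further and conclude that the blood IDUA secondary endpoint as a whole tracks the graft. The documents do not support that: plasma is a separate parameter that is not directly affected, and stable chimerism contributes nothing to change. Nor do they give a basis for carrying the point over to the urine GAG table (14.2.2).

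The change is still worth making. The affected output is planned, the cohorts are very small, and the remedy uses data already collected.

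**What to change.** - **SAP 8.2.1 and Table 14.2.1:** restrict the leukocyte IDUA summary, observed and change, to subjects without prior HSCT, and say so in the title or a footnote. Leave the plasma summary as it is, with all subjects.
- **Listing 16.2.9.3:** show post-HSCT subjects individually, with HSCT status and donor chimerism by lineage at the visits where it was measured (Baseline, Weeks 12 and 48, Month 36/EOS or early termination). Do not carry chimerism values across to other visits.
- **SAP 8.2.1:** state that plasma IDUA is the interpretable blood readout for post-HSCT subjects.

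The cost is SAP and shell wording. HSCT history and chimerism are already collected, so no new assessment is needed. The downside is a smaller leukocyte row, which in a small cohort may be empty; the listing then carries the information. If no transplanted subject enrolled, the rule changes nothing.
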